11.4.3. Expediting Reporting Requirements for Serious Adverse Events

All serious adverse events and AESIs (initial and follow-up information) will be reported on FDA Medwatch (Form 3500A) or Suspect Adverse Event Report (CIOMS Form 1) IRB Reporting Form and sent via email ([contact]) or [contact]) to Pharmacyclics Drug Safety, Pharmacovigilance & Epidemiology (DSP&E) or designee, within 24 hours of the event. Pharmacyclics may request follow-up and other additional information from the Sponsor Investigator.

All SAEs that have not resolved by the end of the study, or that have not resolved upon discontinuation of the subject's participation in the study, must be followed until any of the following occurs:

- The event resolves
- The event stabilizes
- The event returns to baseline, if a baseline value/status is available
- The event can be attributed to agents other than the study drug or to factors unrelated to study conduct.
- It becomes unlikely that any additional information can be obtained (subject or health care practitioner refusal to provide additional information, lost to follow up after demonstration of due diligence with follow-up efforts)

The Sponsor assumes responsibility for appropriate reporting of AEs to the regulatory authorities and governing bodies according to the local regulations.

The investigator (or Sponsor where required) must report these events to the appropriate Independent Ethics Committee/Institutional Review Board (IEC/IRB) that approved the protocol unless otherwise required and documented by the IEC/IRB.

11.4.4. Pregnancy

Before study enrollment, subjects must agree to take appropriate measures to avoid pregnancy. However, should a pregnancy occur in a female study subject, consent to provide follow-up information regarding the outcome of the pregnancy and the health of the infant until 30 days old will be requested.

A female subject or female partner of a male subject must immediately inform the investigator if she becomes pregnant from the time of consent to 90 days after the last dose of study drug(s). Any female subjects receiving study drug(s) who become pregnant must immediately discontinue study drug. The investigator should counsel the subject, discussing any risks of continuing the pregnancy and any possible effects on the fetus.

Although pregnancy itself is not regarded as an AE, the outcome will need to be documented. Any pregnancy occurring in a female subject or female partner of a male subject must be reported from the time of first dose up until 90 days after the last dose of study drug(s). Any occurrence of pregnancy must be recorded on the Pregnancy Report Form Part I and sent via email or fax to Pharmacyclics Drug Safety, Pharmacyclics Drug Safety, Pharmacovigilance & Epidemiology (DSP&E) or designee, per SAE reporting timelines of learning of the event. All pregnancies will be followed for outcome, which is defined as elective termination of the pregnancy, miscarriage, or delivery of the fetus. For pregnancies with an outcome of live birth, the newborn infant will be followed until 30 days old by completing the Pregnancy Report Form Part II. Any congenital anomaly/birth defect noted in the infant must be reported as a SAE.

11.4.5. Other Malignancies

All new malignant tumors including solid tumors, skin malignancies and hematologic malignancies will be reported for the duration of study treatment and during any protocol-specified follow-up periods including post-progression follow-up for overall survival. If observed, enter data in the corresponding eCRF.

11.4.6. Adverse Events of Special Interest (AESI)

Specific AEs, or groups of AEs, will be followed as part of standard safety monitoring activities by the Sponsor. These events (regardless of seriousness) should be reported on the Serious Adverse Event Report Form and sent via email or fax to Pharmacyclics Drug Safety, Pharmacovigilance & Epidemiology (DSP&E) or designee, within 24 hours of awareness.

11.4.6.1. Major Hemorrhage

Major hemorrhage is defined as any of the following:

- Any treatment-emergent hemorrhagic AEs of Grade 3 or higher*.
- Any treatment-emergent serious adverse events of bleeding of any grade
- Any treatment-emergent central nervous system hemorrhage/hematoma of any grade

*All hemorrhagic events requiring transfusion of red blood cells should be reported as Grade 3 or higher AE per CTCAE v5.0

Events meeting the definition of major hemorrhage will be captured as an event of special interest according to [Section 11.4.6](#) above.

12. STUDY ADMINISTRATION AND INVESTIGATOR OBLIGATIONS

12.1. Institutional Review Board (IRB), Research Ethics Board (REB) and Independent Ethics Committee (IEC) Approval

The study will be conducted in accordance with applicable regulatory requirement(s) and will adhere to GCP standards. The IRB/IEC will review all appropriate study documentation in order to safeguard the rights, safety and well-being of the patients. The study will be conducted only at sites where IRB/IEC approval has been obtained. The protocol, Investigator's Brochure, informed consent form, advertisements (if applicable), written information given to the patients (including diary cards), safety updates, annual progress reports, and any revisions to these documents will be provided to the IRB/IEC by the investigator. Pharmacyclics may request that informed consent documents be reviewed by Pharmacyclics or designee prior to IRB/IEC submission.

12.2. Informed Consent

After the study has been fully explained, written informed consent will be obtained from either the patient or his/her guardian or legal representative before study participation. The method of obtaining and documenting the informed consent and the contents of the consent must comply with the ICH-GCP and all applicable regulatory requirements.

12.3. Protected Subject Health Information Authorization

In order to maintain patient privacy, all data capture records, drug accountability records, study reports and communications will identify the patient by initials and the assigned patient number. If requested, the investigator will grant monitor(s) and auditor(s) from Pharmacyclics or its designees and regulatory authority(ies) access to the patient's original medical records for verification of data gathered on the data capture records and to audit the data collection process.

The patient's confidentiality will be maintained and will not be made publicly available to the extent permitted by the applicable laws and regulations.

12.4. Study Files and Record Retention

The investigator will maintain all study records according to the ICH-GCP and applicable regulatory requirement(s).

12.5. Investigational Study Drug Accountability

Accountability for the study drug at all study sites is the responsibility of the principal investigator. The investigator will ensure that the drug is used only in accordance with this protocol. Drug accountability records indicating the drug's delivery date to the site, inventory at the site, use by each patient, and amount returned to Pharmacyclics or a designee or disposal of the drug (if applicable and if approved by Pharmacyclics) will be maintained by the clinical site. Accountability records will include dates, quantities, lot numbers, expiration dates (if applicable), and patient numbers.

12.6. Study Monitoring/Audit Requirements

Regulatory authorities, the IEC/IRB and/or Pharmacyclics may request access to all source documents, data capture records, and other study documentation for on-site audit or inspection. Direct access to these documents must be guaranteed by the investigator, who must provide support at all times for these activities.

12.7. Investigator Responsibilities

The investigator will conduct the study in compliance with the protocol given approval/favorable opinion by the IRB/IEC and the appropriate regulatory authority(ies). Changes to the protocol will require approval from Pharmacyclics and written IRB/IEC approval/favorable opinion prior to implementation, except when the modification is needed to eliminate an immediate hazard(s) to patients. The IRB/IEC may provide, if applicable regulatory authority(ies) permit, expedited review and approval/favorable opinion for minor change(s) in ongoing studies that have the approval /favorable opinion of the IRB/IEC. The investigator will submit all protocol modifications to Pharmacyclics and the regulatory authority(ies) in accordance with the governing regulations.

Any departures from the protocol must be fully documented in the source documents.

12.8. Protocol Amendments

Any amendments to the Protocol or Informed Consent Form must be sent to Pharmacyclics for review and approval prior to submission to the IRB. Written verification of IRB approval will be obtained before any amendment is implemented.

12.9. Publication of Study Results

The Investigator is required to submit to Pharmacyclics a copy of a planned publication (abstract, poster, oral presentation or manuscript) prior to the submission thereof for publication or disclosure. Pharmacyclics may provide scientific comments and suggestions understanding that the Investigator has sole editorial responsibility, and retains the authority to make the final determination on whether or not to incorporate Pharmacyclics comments or requests for additional information.

12.10. Study Discontinuation

Patients may be withdrawn from the study if:

- The patient requests withdrawal.
- If the patient develops side effects that are considered life-threatening
- If the patient refuses to have treatment as recommended.
- If the patient refuses to have tests that are needed to determine whether the treatment is safe and effective.
- If the agents used in this study cease to be available.
- If other causes prevent continuation of the study
- For any other reason that the physician feels it may be necessary that the patient discontinue the study

12.11. Study Completion

The study is expected to be completed approximately 1 year from last subject enrolled, the time point all subjects have exited the study for any reason, or study termination at the Sponsor's discretion, whichever occurs first.

14. APPENDICES

Appendix A. Schedule of Assessments

Study Day	Screening (within 7 days)	Day 1	Day 7 (+/- 3 days)	Month 1 (+/- 7 days)	Month 2 (+/- 7 days)	Month 3 (+/- 7 days)	Month 6 (+/- 7 days)	Month 9 (+/- 7 days)	Month 12 (+/- 7 days)
Informed Consent	X								
Eligibility Confirmation	X								
Ibrutinib 420mg daily ¹		X		Continuous daily dosing Dispensed on D1 of each cycle through Cycle 12					
Rituximab 375mg/m ²			X ²					X ³	
Medical History	X			X	X	X	X	X	X
Physical Exam w/vitals	X			X	X	X	X	X	X
Schirmer's test	X			X	X	X	X	X	X
Karnofsky Performance Status	X								
Serum Pregnancy	X								
Hepatitis serologies	X								
Fasting Lipid Panel	X								
CBC w/differential	X	X	X	X	X	X	X	X	X
Comprehensive Metabolic Panel ⁴	X	X	X	X	X	X	X	X	X
IgG level	X					X	X	X	X
CRP	X			X	X	X	X	X	X
CK	X			X	X	X	X	X	X
LDH	X			X	X	X	X	X	X
Biomarkers (Correlative studies)	X			X	X	X	X	X	X
Concomitant Medications	X			X	X	X	X	X	X
GVHD assessment ⁵	X			X	X	X	X	X	X
GVHD patient self-report form ⁶	X			X	X	X	X	X	X
Pulmonary Function Test	X					X	X	X	X
Calculate cumulative steroid dose				X	X	X	X	X	X
Any new systemic IST				X	X	X	X	X	X
Any IVIG therapy				X	X	X	X	X	X
Adverse Event				X	X	X	X	X	X

¹Dose reduction required when using strong Cyp 3A4 inhibitors (e.g. voriconazole or posaconazole, see Section 6.2.1, table 4) or with hepatic impairment (see Section 5.1.1.5, table 3).

²Rituximab induction 375mg/m² Q7days x 4 doses.

³Rituximab maintenance 375mg/m² q 3months (+/-7days) x 4 doses.

⁴Glucose, BUN, creatinine, total bilirubin, alkaline phosphatase, albumin, SGOT (AST), SGPT (ALT), calcium, magnesium

⁵See appendix E

⁶See appendix F

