5.1.1.2. Dose and Administration

Ibrutinib 420 mg (3 x 140-mg capsules) is administered orally once daily. It is expected that many subjects commencing therapy for cGVHD will require anti-fungal prophylaxis. Please see Section 6.2.1 for dose modification guidelines with concomitant use of CYP3A inhibitors.

The capsules are to be taken around the same time each day with 8 ounces (approximately 240 mL) of water. The capsules should be swallowed intact and subjects should not attempt to open capsules or dissolve them in water. The use of strong CYP3A inhibitors/inducers (other

than those specifically permitted on study), and grapefruit and Seville oranges should be avoided for the duration of the study ([Appendix C](#)).

If a dose is not taken at the scheduled time, it can be taken as soon as possible on the same day with a return to the normal schedule the following day. The subject should not take extra capsules to make up the missed dose.

The first dose will be delivered in the clinic on Day 1, after which subsequent dosing is typically on an outpatient basis. Ibrutinib will be dispensed to subjects in bottles at each visit. Study drug may not be shipped to the subject without approval from PCYC and may not be dispensed to anyone other than the subject. Unused ibrutinib dispensed during previous visits must be returned to the site and drug accountability records ([Section 12.5](#)) updated at each visit. Returned capsules must not be redispensed to anyone.

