5.1.1.4. Dose Modification for Non-Cardiac Adverse Reactions

The dose of study drug must be modified according to the dose modification guidance in [Table 1](#) and [Table 2](#) if any of the following non-cardiac toxicities occur:

- Grade 4 neutropenia (ANC <500/ μ L) for more than 7 days. See [Section 6.1](#) for instructions regarding the use of growth factor support.
- Grade 3 thrombocytopenia (platelets <50,000/ μ L) in the presence of clinically significant bleeding events.
- Grade 4 thrombocytopenia (platelets <25,000/ μ L).
- Grade 3 or 4 nausea, vomiting, or diarrhea if persistent, despite optimal anti-emetic and/or anti-diarrheal therapy.
- Any other Grade 4 or unmanageable Grade 3 non-cardiac toxicity

Adverse events that are considered related to concomitant high dose corticosteroids (e.g. hyperglycemia, insomnia) do not require dose modification or holding of ibrutinib.

If the dose of ibrutinib is reduced, at the investigator's discretion, the dose of ibrutinib may be re-escalated after 4 weeks of a dose reduction in the absence of a recurrence of the toxicity that led to the reduction. Dose changes must be recorded in the CRF.

Table 1. Ibrutinib Dose Modifications

Occurrence	Action to be Taken
First	Withhold study drug until recovery to Grade ≤ 1 or baseline; may restart at original dose level
Second	Withhold study drug until recovery to Grade ≤ 1 or baseline; may restart at 1 dose level lower (i.e., 280 mg/day for 420 mg/day dose)
Third	Withhold study drug until recovery to Grade ≤ 1 or baseline; may restart at 1 dose level lower (i.e., 140 mg/day for 420 mg/day dose; 280 mg/day)
Fourth	Discontinue study drug

Table 2. Ibrutinib Dose Reduction Levels

Starting Dose Level	140 mg	280 mg	420 mg
Dose Reduction Level 1	70 mg	140 mg	280 mg
Dose Reduction Level 2	Discontinue	70 mg	140 mg
Dose Reduction Level 3	NA	Discontinue	Discontinue

For required dose modification for hepatic impairment refer to [Section 5.1.1.5](#) and for concomitant treatment with CYP3A inhibitors refer to [Section 5.1.1.6](#).

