5.1.1.7. Dose Modification for Concomitant Use of CYP3A Inhibitors

Dose adjustment of ibrutinib secondary to concomitant use of CYP 3A4 inhibitors should follow Table 4. Concomitant use of strong CYP inhibitors is not permitted in subjects with chronic hepatic impairment.

Table 5. Dose Modification Guidance for CYP3A4 Inhibitors

Co-administered Drug	Recommended Ibrutinib Dose for the Duration of the Inhibitor Use
Mild CYP3A4 inhibitors	420 mg once daily. No dose adjustment required.
Moderate CYP3A4 inhibitors	420 mg once daily. No dose adjustment required.
Voriconazole Posaconazole at doses less than or equal to suspension 200 mg BID or delayed-release tablet 300mg QD	280 mg once daily.
Posaconazole at higher doses	140 mg once daily.
Other strong CYP3A4 inhibitors	Avoid concomitant use. If these inhibitors will be used short term (such as anti-infectives for seven days or less), interrupt IMBRUVICA.

After discontinuation of a CYP3A4 inhibitor, resume previous dose of ibrutinib.

If Bili $>$ 1.5 x ULN, avoid and/or discontinue voriconazole, posaconazole, or other strong CYP3A4 inhibitor.

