6.2. Medications to be Used with Caution

6.2.1. CYP3A Inhibitors/Inducers

Ibrutinib is metabolized primarily by CYP3A4. Concomitant use of ibrutinib with drugs that strongly or moderately inhibit CYP3A4 can increase ibrutinib exposure. Dose adjustment of ibrutinib due to concomitant use of CYP3A4 inhibitors should follow Table 4 (Section 5.1.1.6)

Avoid concomitant use of systemic strong CYP3A4 inducers (e.g., carbamazepine, rifampin, phenytoin, and St. John's Wort). Consider alternative agents with less CYP3A4 induction.

A list of common CYP3A4 inhibitors and inducers is provided in [Appendix C](#). For further information, please refer to the current version of the [IB](#) and examples of inhibitors, inducers, and substrates can be found at <http://medicine.iupui.edu/clinpharm/ddis/main-table/>. This website is continually revised and should be checked frequently for updates.

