Appendix C. Inhibitors and Inducers of CYP3A

Inhibitors and inducers of CYP3A enzymes are defined as follows. Refer to [Section 6.2.1](#) on instructions for concomitant use of CYP3A inhibitors and inducers with ibrutinib. Further information can be found at the following website: <http://medicine.iupui.edu/clinpharm/ddis/main-table/>.

Inhibitors of CYP3A	Inducers of CYP3A
Strong inhibitors:	
boceprevir	carbamazepine
clarithromycin	barbiturates
cobicistat	efavirenz
indinavir	glucocorticoids
itraconazole	modafinil
ketoconazole	nevirapine
mibefradil	oxcarbazepine
nefazodone	phenobarbital
nelfinavir	phenytoin
posaconazole ^a	pioglitazone
ritonavir	rifabutin
saquinavir	rifampin
suboxone	St. John's Wort
telaprevir	troglitazone
telithromycin	
troleanomycin	
Moderate inhibitors:	
amiodarone	
amprenavir	
aprepitant	
atazanavir	
ciprofloxacin	
crizotinib	
darunavir	
diltiazem	
dronedarone	
erythromycin	
fluconazole	
fosamprenavir	
grapefruit juice	
imatinib	
Seville orange juice	
verapamil	
voriconazole ^a	
Weak inhibitors:	
cimetidine	
fluvoxamine	
All other inhibitors:	
chloramphenicol	
delavirdine	
diethyl-dithiocarbamate	
gestodene	
mifepristone	
norfloxacin	
norfluoxetine	
star fruit	

^a Classification based on internal data.

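### Appendix A footnote 1 calls for an ibrutinib dose reduction with any strong CYP3A4 inhibitor, but Table 5 reduces only for voriconazole and posaconazole, and the footnote's references lead to the wrong dosing tables.

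*Combined protocol and SAP*

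**What the plan says.** **Footnote 1, Appendix A.** Attached to the ibrutinib row, it makes dose reduction a requirement with strong CYP3A4 inhibitors. An e.g. introduces two drugs and the reference: "voriconazole or posaconazole, see Section 6.2.1, table 4". For hepatic impairment it refers to Section 5.1.1.5, table 3.

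**Table 5, Section 5.1.1.7.** Voriconazole, and posaconazole up to 200 mg BID suspension or 300 mg QD delayed-release tablet, call for 280 mg of ibrutinib daily. Posaconazole at higher doses calls for 140 mg. Other strong inhibitors have no reduced dose: "Avoid concomitant use. If these inhibitors will be used short term (such as anti-infectives for seven days or less), interrupt IMBRUVICA".

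**Supporting text.** Section 5.1.1.2 says that strong CYP3A inhibitors other than those the study permits are to be avoided throughout. Exclusion 24 bars strong inhibitors within 7 days before the first dose, or as continuous treatment, and exempts only voriconazole and posaconazole.

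**References to the CYP3A rule.** Section 5.1.1.2: "Please see Section 6.2.1 for dose modification guidelines with concomitant use of CYP3A inhibitors". Appendix C sends the reader to the same section "on instructions for concomitant use of CYP3A inhibitors and inducers with ibrutinib". Section 6.2.1 forwards the reader: "Dose adjustment of ibrutinib due to concomitant use of CYP3A4 inhibitors should follow Table 4 (Section 5.1.1.6". Section 5.1.1.4 says "for concomitant treatment with CYP3A inhibitors refer to [Section 5.1.1.6". The sentence above Table 5 reads "Dose adjustment of ibrutinib secondary to concomitant use of CYP 3A4 inhibitors should follow Table 4".

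**The concern.** The schedule's ibrutinib row covers dispensing through Cycle 12, so its footnote is a natural place for staff to look when a patient is started on an interacting drug. For a strong inhibitor other than the two azoles, reducing ibrutinib is a different action from avoiding the inhibitor or stopping ibrutinib while it is given. Section 6.2.1 states that strong inhibition can raise ibrutinib exposure, so a patient kept on any dose where Table 5 calls for interruption could be over-exposed. Exclusion 24 screens at entry and does not direct staff when a new course starts on study. Table 5 itself anticipates such courses, giving short anti-infective treatment as its example.

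**Working it through.** No formula applies. The check compares the instructions and then follows the references.

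**1. The instructions**

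| Co-administered drug | Footnote 1 | Table 5 |
|---|---|---|
| Voriconazole | Reduce | 280 mg |
| Posaconazole, up to the stated doses | Reduce | 280 mg |
| Posaconazole, higher doses | Reduce | 140 mg |
| Any other strong inhibitor | Reduce (no dose given) | Avoid; interrupt ibrutinib if short term |

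The first three rows agree and the last does not. Appendix C lists 16 strong inhibitors. Posaconazole is the only one of them with a reduced dose in Table 5, which leaves 16 − 1 = 15 names, such as clarithromycin and itraconazole, in the last row. Voriconazole is classed as moderate in Appendix C but has its own entry in Table 5, so it is not in conflict. The 15 shows how far the wording reaches and says nothing about how often it would matter.

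**2. Which text is wrong**

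Section 5.1.1.2 and exclusion 24 both treat voriconazole and posaconazole as the only permitted strong inhibitors. They match Table 5, so the footnote is the error and no new clinical decision is needed.

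**3. Where the CYP3A references lead**

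| Place | Cites | Leads to |
|---|---|---|
| Appendix A, footnote 1 | 6.2.1, Table 4 | Hepatic table |
| 6.2.1 | Table 4, 5.1.1.6 | Hepatic table and section |
| 5.1.1.4 | 5.1.1.6 | Hepatic section |
| 5.1.1.7 | Table 4 | Hepatic table by number, but Table 5 is directly below |
| 3.1 (shared with hepatic) | 5.1.1.5 and 5.1.1.6 | Cardiac and hepatic sections |
| 5.1.1.2 and Appendix C | 6.2.1 | Right section, which then forwards to the wrong table |

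**4. Where the hepatic references lead**

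Section 5.1.1.4 says "For required dose modification for hepatic impairment refer to [Section 5.1.1.5", which is now the cardiac section. Section 5.1.1.6 cites Table 3 for its own rule, but Table 3 is cardiac and its own table is Table 4. Footnote 1 cites Section 5.1.1.5, table 3, which is cardiac on both counts.

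Every wrong number is one too low. That is what would result if the cardiac section and table (5.1.1.5, Table 3) were inserted and the later references were not renumbered.

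**The case against.** The strongest reply is that this is a loose e.g. where i.e. was meant. The footnote's two examples are exactly the two permitted drugs. It states no dose, so staff must consult the dose table to act on it, and the CYP3A table contains the avoid-or-interrupt row. Section 5.1.1.2 says, for the whole study, that other strong inhibitors are to be avoided. The List of Tables titles Table 5 correctly, and the wrong reference in Section 5.1.1.7 sits directly above it.

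Most of this stands and is why the point is minor. It does not remove the conflict: the footnote as written covers the class, and the reference meant to lead to the dose table leads to the hepatic one.

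A reader might infer four stronger things that the documents do not support:

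- **That the footnote sets a rival regimen, telling staff to continue at a specified lower dose.** It gives no dose and does not say to continue; continuing is only what a reduction implies.
- **That 15 of 16 measures the risk.** It counts drug names. The documents give no expected frequency of use, so neither common nor rare exposure can be asserted.
- **That the CYP3A rule cannot be found.** Sections 5.1.1.2 and Appendix C take a valid step to 6.2.1, and Section 5.1.1.7 contains Table 5.
- **That the synopsis and Section 3.1 make the same error.** They speak of dose adjustment, which can include interruption. That is ambiguous but not wrong; only the footnote says reduction.

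**Conclusion.** The conflict is real and is wrong as written. For strong CYP3A4 inhibitors other than voriconazole and posaconazole, footnote 1 says reduce, while the governing table says avoid, or interrupt if use is for seven days or less. The footnote's CYP3A and hepatic references each lead to a dosing table for a different problem. It is worth correcting because it is an operative dosing instruction with a safety consequence if followed literally. It remains minor because Table 5, Section 5.1.1.2 and exclusion 24 agree with one another.

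No milligram discrepancy can be calculated, since the footnote names no dose. Sample size, power and the primary analysis are unaffected. The conclusion assumes that Table 5 states the intended rule, which the two agreeing sections support.

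**What to change.** Replace footnote 1 with: *Dose reduction required with voriconazole or posaconazole; avoid other strong CYP3A4 inhibitors, or interrupt ibrutinib if they are used short term (seven days or less); see Section 5.1.1.7, Table 5. For hepatic impairment see Section 5.1.1.6, Table 4.* The reference to Section 5.1.1.7 also brings in its bilirubin and chronic hepatic impairment restrictions, so the footnote need not repeat them.

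In the same amendment:

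- Point the CYP3A references in 3.1, 5.1.1.4, 5.1.1.7 and 6.2.1 to Section 5.1.1.7 and Table 5. Section 5.1.1.2 and Appendix C can keep citing 6.2.1 once that section is corrected.
- Point the hepatic references in 3.1, 5.1.1.4 and 5.1.1.6 to Section 5.1.1.6 and Table 4.
- Optionally, clarify the dose-adjustment wording in the synopsis and 3.1.

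The cost is a wording amendment only. Treatment policy, data collection and analysis do not change.
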